## **1. Introduction**

This document outlines the detailed statistical methods to be implemented for the data collected within the scope of Endurant Evo US Clinical Trial. This document is designed for internal use as a guideline for study Biostatistician and Statistical Programmer(s). Study protocol is the primary resource if clarification is needed for the contents of this document. Analysis results obtained from the analyses outlined in this document will be the basis of the Clinical Study Report for this study.

As with any statistical analysis plan, the proposed methods and approaches to the data analysis should be viewed as flexible. Changes to the plan may arise if the emerging picture suggests that deviations from the original plan would provide a more reliable and valid analysis of the data. The purpose of this plan is to provide general, and in some instances, specific guidelines from which the analysis will proceed. Nonetheless, sound statistical reasoning must substantiate deviations from these guidelines.

## **2. Study Objectives**

The purpose of the Endurant Evo US Clinical Trial is to demonstrate that the Endurant Evo Abdominal Aortic Aneurysms (AAA) Stent graft system is safe and effective for endovascular treatment of infrarenal abdominal aortic or aortoiliac aneurysms. The clinical evidence collected as part of this trial will be used in conjunction with data collected during the concurrently enrolling Endurant Evo International Clinical Trial to support Pre-Market Application (PMA) Approval of the Endurant Evo AAA Stent graft system.

The primary safety objective is to demonstrate the safety of the Endurant Evo AAA Stent graft system for the endovascular treatment of abdominal aortic or aortoiliac aneurysms. Safety will be assessed through the proportion of subjects who have a Major Adverse Events (MAE) reported within 30-days post-implantation.

The primary effectiveness objective is to demonstrate successful delivery and deployment of the Endurant Evo AAA Stent graft system with successful removal of the delivery system during the index procedure as well as the treatment success at 12 months.

Secondary objectives include descriptive analyses of secondary endpoints as well as acute procedural and clinical utility measures.

## **3. Study Design**

The Endurant Evo US Clinical Trial is a prospective, multi-center, pre-market, non-randomized, single-arm trial.

### **3.1. Treatment and Subject Enrollment**

The study population will include those subjects who are appropriate candidates for endovascular repair of infrarenal abdominal aortic or aortoiliac aneurysms, and who meet the Inclusion/Exclusion criteria (defined in the Clinical Investigation Plan Section D).

For subjects that are treated with the bifurcated stent graft minimal 3 pieces will be implanted in the target segment; one bifurcated stent graft component and 2 limb stent graft components. For subjects that are treated with the Aorto-Uni-Iliac (AUI) component approximately 2 pieces will be implanted in the target segment; the AUI stent graft component and one limb stent component. Additional stent graft extensions might be needed to cover the complete target lesion length.

Globally, a total of 140 subjects will be concurrently enrolled in the United States and outside the United States to support the primary endpoints. Up to 50% of subject data used to support PMA approval may come from subjects enrolled at sites outside of the US under a separate CE Mark study protocol; called the Endurant Evo International Clinical Trial protocol.

The Endurant Evo International Clinical Trial protocol and Endurant Evo US Clinical Trial protocol will be identical with respect to the inclusion/exclusion criteria, and follow up data collection.

Subjects will have required follow-up evaluations at the following time points:

- 1 month following the index procedure
- 6 months following the index procedure
- 12 months following the index procedure

Subjects will be followed until the last subject enrolled has completed the 1 year follow-up visit or until PMA approval is obtained in the US (whatever is later), however, Medtronic will work with FDA to determine if longer term follow after PMA approval is required.

The Endurant Evo Global Clinical program will be conducted at up to 30 sites worldwide with up to 20 sites participating under the Endurant Evo US Clinical trial protocol in the United States and with approximately 10 sites participating under the Endurant Evo International Clinical trial protocol outside the United States. In the United States, a minimum of 70 subjects will be enrolled at up to 20 investigational sites. Investigators at any single site may not enroll more than 20% of the total global enrollment (140 subjects) in the trial.

The total enrollment period is not expected to exceed 12 months. However, if a minimum of 50 high angulation indication subjects are not enrolled as part of the first 140 subject cohort, Medtronic will submit the PMA application to obtain approval for the 60°angulation indication with the 140 subject cohort data. In this event, Medtronic will continue enrollment for the high angulation indication and as result the total enrollment may be extended up to 2 years.

### **3.2. Analysis Strategy**

The Endurant Evo US Clinical Trial will focus on balancing pre- and post-market clinical data to establish safety and effectiveness. Study success is defined as rejecting the null hypothesis for the primary safety endpoint test ( $\geq 20\%$ ), with a condition upon rejecting the null hypothesis for the post-market primary effectiveness test ( $\leq 80\%$ ). As such, the following analyses will be submitted:

- Pre-market: 30-day primary safety endpoint (hypothesis based, see 8.4)
- Pre-market: 6-month effectiveness analysis (descriptive)
- Post-market: 12-month primary effectiveness endpoint (hypothesis based, see 8.4)

The proposed clinical strategy described in this section will allow for appropriate evaluation of the safety and effectiveness of the Endurant Evo AAA stent graft system. Safety will be established through the hypothesis-based primary safety endpoint at 30 days. Reasonable assurance of effectiveness will be provided via the pre-market 6-month analysis and then confirmed at the 12-month post-market primary effectiveness endpoint.

### 3.3. Sample Size Consideration

The sample size for the Endurant Evo global program is calculated for both the primary safety endpoint and the primary effectiveness endpoint.

It is expected that the Endurant Evo AAA stent graft system will result in a MAE rate at 10% with respect to the primary safety endpoint and 90.5% treatment success for the primary effectiveness endpoint according to its predicates' performances shown in Table 1.

In order to pass both hypothesis tests with an overall study power of 80%, a sample size of 119 evaluable subjects will be required to pass each hypothesis with 90% statistical power (target significance level is 0.025.) To account for attrition of 15% (85% imaging compliance) at 12 months, 140 subjects will be enrolled globally to ensure at least 119 evaluable subjects. Note that a minimum of 50 subjects will be enrolled with the high neck angulation indication and a minimum of 70 subjects will be enrolled with percutaneous access. If a minimum of 50 high angle indication subjects are not enrolled as part of the first 140 subject cohort, Medtronic will continue enrollment for the high angulation indication but submit the PMA application to obtain approval for the 60° angulation indication with the 140 subject cohort data.

Table 1: Clinical Data from Talent AAA eLPS and Endurant Studies

Predicates	MAE within 30 Days	Successful Aneurysm Treatment at 12 Months
Talent AAA eLPS Arm	11% (18/166)	86% (107/125)
Endurant IDE Bifurcated Arm	4% (6/150)	95% (115/121)
Endurant IDE AUI Arm	11% (5/44)	97% (35/36)

## 4. Analysis Sets

### 4.1. Primary analysis set

The primary analysis set will consist of the Intent-to-Treat (ITT) population. This analysis set is defined as all subjects who were enrolled. The subject will be considered to be enrolled when arterial access has been established with an attempt to introduce the Endurant Evo AAA stent graft.

### 4.2. Secondary analysis set

A secondary analysis set will be the Per-Protocol population. This analysis set is comprised of all ITT subjects who met inclusion and exclusion criteria, received the test device, and completed 12- month follow-up (including death but excluding withdrawal or lost to follow-up subjects within the 12- month follow-up period).

 Results are from the Talent AAA (Talent AAA Control data referenced in Endurant Clinical Study Report, Appendix 2 of M090018\_M005 Clinical Module), Endurant (P100021) PMA 90-day update submission submitted via P100021/A002, and Endurant PMA supplement via P100021/S021. The results on successful aneurysm treatment are reported at 12 months and included all occlusions through the time period

#### 4.3. Subsets

Subset analyses by-sex, by-race (based on subjects enrolled in the US only, since collection of race and ethnicity data may not be allowed outside the US as per local law and regulation), and by-region/study site will be performed on the primary safety and effectiveness endpoints using descriptive statistics and reviewed for clinical significant difference.

In addition to the full cohort analyses, separate descriptive analyses on the AUI sub-group and percutaneous access subgroup will be provided in the PMA submission. Percutaneous or surgical cut-down is the access method used for delivering the main section or AUI device.

Subset analysis of the subjects treated with percutaneous access vs. surgical cut-down will be compared on various access site complications and conversions to a different access site or type of access.

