### C.5 Study Design

The Endurant Evo US Clinical Trial is prospective, multi-center, pre-market, non-randomized, single-arm trial. The trial is designed to assess the clinical safety and performance of the Endurant Evo AAA Stent graft system.

Globally, a total of 140 subjects will be concurrently enrolled in the United States and outside the United States to support the primary endpoint. Up to 50% of subject data used to support PMA approval may come from subjects enrolled at sites outside of the US under a separate CE Mark study protocol; the Endurant Evo International Clinical Trial protocol. The Endurant Evo International Clinical Trial protocol and Endurant Evo US Clinical Trial protocol will be identical with respect to the inclusion/exclusion criteria, and follow up data collection.

Given the UADEs that have occurred within the Endurant Evo study (transition stent fracture, partial suprarenal stent detachment, and suprarenal stent fracture), enrollment was terminated. Total global enrollment, upon termination, was 139 subjects. This includes 70 subjects enrolled in the United States and 69 enrolled outside the United States.

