### C.7 Sample Size

The sample size for the Endurant Evo global program is calculated for both the primary safety endpoint and the primary effectiveness endpoint.

It is expected that the Endurant Evo AAA stent graft system will result in a MAE rate at 10% with respect to the primary safety endpoint and 90.5% treatment success for the primary effectiveness

 A minimum of 50 subjects will be enrolled with the high neck angulation indication (defined as proximal neck length  $\geq 15$  mm, infrarenal neck angulation  $> 60^\circ$  and  $\leq 75^\circ$  and suprarenal neck angulation  $\leq 60^\circ$ ). If a minimum of 50 subjects are not enrolled as part of the first 140 subject cohort, Medtronic will continue enrollment for the high angulation indication but submit the PMA application to obtain approval for the 60°angulation indication with the 140 subject cohort data. A minimum of 70 subjects enrolled in the study will have percutaneous access.

endpoint according to its predicates' performances shown in Table C-1.

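### SAP 4.3 groups subjects by the access route that delivered the main device, so a percutaneous conversion before delivery cannot appear in the percutaneous group

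*SAP*

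**What the plan says.** SAP 4.3 (Subsets) announces that "separate descriptive analyses on the AUI sub-group and percutaneous access subgroup will be provided in the PMA submission". It then defines the access variable: "Percutaneous or surgical cut-down is the access method used for delivering the main section or AUI device". The next paragraph says that the percutaneous and cut-down subjects "will be compared on various access site complications and conversions to a different access site or type of access".

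Protocol C.7, in a footnote, sets a floor for one of the groups: "A minimum of 70 subjects enrolled in the study will have percutaneous access". SAP 3.3 repeats it.

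Three other provisions bear on the point:

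- **Enrolment.** A subject is enrolled once there is arterial access and an attempt has been made to introduce the stent graft (Protocol F.1, SAP 4.1). Adverse event assessment starts at that moment (Protocol F.2.1).
- **Non-delivery.** Protocol F.1 and F.2.1.2 foresee enrolled subjects in whom the device is not implanted.
- **Attribution.** Neither document groups subjects by planned or first-attempted access, or says which group a conversion before delivery belongs to.

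**The concern.** The group label is fixed after the access attempt, and one of the outcomes compared is a change of access type. Membership therefore depends partly on the outcome. Take a subject in whom the device is first tried percutaneously, who is then converted to cut-down, and whose main section is delivered through the cut-down. Under the SAP sentence this is a cut-down subject, and the conversion, with any complication of the failed attempt, is reported in the cut-down column. What remains in the percutaneous group is the subjects in whom percutaneous access lasted until main-device delivery.

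At stake is a descriptive result, but one that the programme had reason to want. A lower-profile delivery system is a design target (Protocol B.1), percutaneous access and fewer access complications are listed among the potential benefits (Protocol J.2), and a minimum number of percutaneous subjects was set. SAP 4.3 is the only place where outcomes are compared between the two routes.

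**Working it through.** The documents state no rate, power or sample size for this comparison, so there is no figure of the plan to reproduce. What follows is direct counting under stated assumptions.

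**Inputs from the documents.** The percutaneous minimum is 70 (SAP 3.3: "a minimum of 70 subjects will be enrolled with percutaneous access"). Enrolment was 139 (Protocol C.5: "Total global enrollment, upon termination, was 139 subjects"). If 70 started percutaneously, 139 − 70 = 69 started by cut-down. The actual split is not given, so 70/69 is only an illustration.

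**Assumed inputs.** Let A = percutaneous starts, C = cut-down starts, c = percutaneous-to-cut-down conversions after enrolment and before main-device delivery, and d = conversions at or after delivery. Each subject converts at most once, and nobody moves from cut-down to percutaneous.

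**Step 1: direction for conversions.** The percutaneous conversion rate is (c + d)/A by first-attempted route and d/(A − c) under SAP 4.3. The SAP figure is the smaller one when dA < (c + d)(A − c), which simplifies to 0 < c(A − c − d). This holds whenever c is at least 1, unless every percutaneous start was converted. If c = 0, the two rates are equal.

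**Step 2: size for conversions, with A = 70 and C = 69.**

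| c | First route, d = 0 | SAP rule, d = 0 | First route, d = 2 | SAP rule, d = 2 | Moved subjects in cut-down, c/(C + c) |
|---|---|---|---|---|---|
| 0 | 0/70 = 0% | 0/70 = 0% | 2/70 = 2.9% | 2/70 = 2.9% | 0/69 = 0% |
| 2 | 2/70 = 2.9% | 0/68 = 0% | 4/70 = 5.7% | 2/68 = 2.9% | 2/71 = 2.8% |
| 4 | 4/70 = 5.7% | 0/66 = 0% | 6/70 = 8.6% | 2/66 = 3.0% | 4/73 = 5.5% |
| 7 | 7/70 = 10.0% | 0/63 = 0% | 9/70 = 12.9% | 2/63 = 3.2% | 7/76 = 9.2% |
| 10 | 10/70 = 14.3% | 0/60 = 0% | 12/70 = 17.1% | 2/60 = 3.3% | 10/79 = 12.7% |

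The d = 2 columns show that the outcome is understated, not emptied. A 100/39 split gives the same pattern: with c = 7 and d = 0, 7/100 = 7.0% by first route becomes 0/93 = 0%, and 7/46 = 15.2% appears under cut-down.

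**Step 3: complications, with A = 70, C = 69 and c = 7.** Assume a 5% complication risk in all unconverted subjects and a risk r in converted subjects. By first route, percutaneous is (63 × 0.05 + 7r)/70 and cut-down is 5.0%. Under SAP 4.3, percutaneous is 5.0% and cut-down is (69 × 0.05 + 7r)/76.

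- r = 5%: 5.0% in every cell, so there is no bias.
- r = 20%: first route 4.55/70 = 6.5% vs 5.0%; SAP rule 5.0% vs 4.85/76 = 6.4%.
- r = 40%: first route 5.95/70 = 8.5% vs 5.0%; SAP rule 5.0% vs 6.25/76 = 8.2%.

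The order of the groups reverses in the last two cases. That depends on r being above 5% and on the two routes having the same baseline risk. Neither is stated in the documents.

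**Step 4: subjects without a group.** If the main section or AUI is never delivered, no method was used to deliver it. The SAP sentence then assigns the subject nowhere, although the subject is in the ITT set.

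**The case against.** The strongest reply is that the sentence has another purpose. A bifurcated implant has at least three pieces (SAP 3.1), and percutaneous access may be unilateral or bilateral (SAP 5), so one subject can have mixed access. The sentence says which access decides the label. It does not mention conversions, and the table shells, which might settle the matter, are in a separate attachment. This is a fair account of why the sentence is there. It still leaves conversions before delivery either grouped by final route, as the words say, or not assigned at all, and the same correction serves both cases.

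The second reply is that little hangs on it. The comparison has no hypothesis, alpha or power, access is not randomised, and Protocol L.9 records that the PMA submission was withdrawn. All of this stands and limits the importance. Grouping by first route would not make the comparison causal either. But a misassigned descriptive rate is still wrong, and SAP 1 makes these analyses the basis of the Clinical Study Report.

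The third reply concerns events before enrolment. Bleeding or vessel injury that forces a cut-down before any attempt to introduce the stent graft precedes enrolment and the required adverse event assessment. It need not be recorded for either group. The shift of complications described here is therefore clear only for conversions between the first introduction attempt and delivery.

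A reader might also infer that this analysis is the sole evidence on access. It is not: SAP 5 reports percutaneous use, blood loss and transfusion, and Protocol L.2 defines access failure as a device deficiency. None of these compares the two routes, however.

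**Conclusion.** The point holds in a conditional form. As written, SAP 4.3 removes pre-delivery percutaneous conversions from the group they describe, and that group's conversion rate is too low whenever at least one such conversion occurs. Conversions at or after delivery, and percutaneous-to-percutaneous site changes, remain counted. The complication comparison is shifted towards cut-down only if converted subjects have a higher risk.

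A reader might infer that the comparison is certainly biased in favour of percutaneous access, or that its direction will reverse. The documents do not support that. They give no conversion counts, access split or complication risks, and every figure above other than 70 and 139 is assumed or derived from assumptions. With no pre-delivery conversions there is no bias at all. Nor is a percutaneous conversion rate of exactly zero implied, since later conversions still count.

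Enrolled subjects whose main device is never delivered have no access group. The primary endpoints and study success do not depend on this variable.

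**What to change.** In SAP 4.3, replace the defining sentence with wording to this effect: enrolled subjects are grouped by the access method first attempted on the side intended for the main section or AUI, whether or not the device was later delivered by that route; later conversions and access-site complications are attributed to that group. Keep the grouping by delivery route as a supplementary table. Subjects whose main device is never delivered then have a group as well.

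The cost is one sentence and one derived variable. The first route has to be known in any case, because a conversion cannot be identified without it. Percutaneous rates may look slightly less favourable. The change does not bring complications that occur before the first introduction attempt into the required adverse event assessment, and the report should say so.

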### *Endurant Evo Stent Graft*

[figure not shown]
The Endurant Evo stent graft is comprised of the following stent graft configurations:

- Bifurcated component
- Limb component
- Aorto-Uni-Iliac (AUI)
- Aortic extensions
- Iliac extensions

Each stent graft component is introduced separately into the vessel and is mated in vivo to the components already in situ. All components are constructed by sewing the self-expanding nitinol stents to a fabric graft. The suprarenal stents with anchor pins on the proximal end of the bifurcated component, the AUI component and the aortic extension are laser cut from a nitinol tube and all other stents are wire-formed. The stents are formed in a ring with opposing ends being terminated together in crimp sleeves. The suprarenal and wire formed stents are sewn to the polyester (PET) graft fabric using ultra high molecular weight polyethylene (UHMWPE) suture.

The graft fabric is [REDACTED], then cut and seamed into the stent graft component form with PET suture and UHMWPE suture. [REDACTED]

Radiopaque (RO) markers are sewn onto each component of the stent graft to aid in fluoroscopic visualization and to facilitate accurate placement of each component. Endurant Evo uses three types of radiopaque markers: fold-over ("Clip") markers, tube markers, and coil markers. Clip markers are thin pieces of platinum iridium that are folded over the edge of the graft material in order to show exact location of the fabric edge. Tube markers are sectioned pieces of platinum iridium tubing. Coil marker is a coiled Platinum-Iridium wire which outlines the contralateral gate to facilitate gate cannulation. RO markers are located at the proximal and distal ends of each stent graft component, as well as at the bifurcation of the bifurcated stent grafts to help visualize the edges and locations of the stent grafts, indicate overlap distance between mating stent graft components, and indicate orientation of the contralateral gate on the bifurcated stent graft. RO markers are sewn to the graft fabric using UHMWPE suture to optimize both strength and profile. The nitinol stents may also be visualized under fluoroscopy. The Endurant Evo stent graft configurations are shown in Figure 1 below.

1. RO Marker	5. Iliac Extension Configuration
2. RO Gate Marker	6. Limb Configuration
3. Aortic Extension Configuration	7. Aorto-Uni-Iliac Configuration
4. Aortic Bifurcated Configuration	

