  - f) Subject has distal non-aneurysmal iliac (cylindrical) fixation length  $\geq 20$  mm bilateral for the bifur and unilaterally for the AUI

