#### *Additional Observations*

The following acute procedural observations and clinical utility measures will be reported:

- Mean duration (min) of procedure (time between initial skin access to final skin closure)
- Proportion of subjects who underwent general/local/epidural/spinal anesthesia
- Proportion of subjects who underwent unilateral/bilateral percutaneous access
- Proportion of subjects requiring blood transfusions, excluding cell saver
- Mean volume (cc) of estimated blood loss
- Mean duration (min) of radiation exposure
- Radiation exposure (mGy)
- Mean length of time (hours) in intensive care unit
- Mean length of time (days) of hospital stay (from the index procedure to hospital discharge)

Health-related quality of life outcomes will be assessed at baseline, 1-month, 6-month and 12-month follow-up visits using the EQ5D questionnaire

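### The percutaneous versus cut-down comparison labels each subject by the main-device side only, with no category for bifurcated subjects whose two sides were accessed differently

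*SAP*

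**What the plan says.** SAP 4.3 (Subsets) defines the access label: "Percutaneous or surgical cut-down is the access method used for delivering the main section or AUI device". It then states the comparison: "Subset analysis of the subjects treated with percutaneous access vs. surgical cut-down will be compared on various access site complications", together with changes of access site or access type. It gives no rule for which side's events count, no category for subjects with a different method on each side, and no per-site denominator.

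Other places show how many sides are involved:

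- SAP 3.1 says a bifurcated implant has at least three pieces, "one bifurcated stent graft component and 2 limb stent graft components".
- The stent graft description in Protocol B.2.1 says "Each stent graft component is introduced separately into the vessel and is mated in vivo to the components already in situ", and describes a coil marker that "outlines the contralateral gate to facilitate gate cannulation".
- Protocol D.1 sets the distal fixation length at 20 "mm bilateral for the bifur and unilaterally for the AUI".
- SAP 5 (Additional Observations) lists "Proportion of subjects who underwent unilateral/bilateral percutaneous access" as a separate summary.

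SAP 3.3 adds that "a minimum of 70 subjects will be enrolled with percutaneous access". It does not say whether the label in 4.3 decides who counts toward that number.

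**The concern.** The label follows one side of the subject, while the outcome, as worded, covers every access site. Many of the access complications listed in Protocol L.3 (hematoma, pseudoaneurysm, arteriovenous fistula, dissection, infection) belong to a particular site. Take a bifurcated subject whose main body went in percutaneously and whose contralateral limb went in through a cut-down. A hematoma at the cut-down groin would appear in the percutaneous column. The reverse happens when the main side was cut down.

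Mixed subjects make the two columns more alike than the two methods are. That matters to some degree here, because Protocol J.2 lists fewer access complications and the ability to use percutaneous access among the potential benefits. A table that understates a difference between methods, in either direction, would inform that question less well. No hypothesis test or success criterion uses the comparison.

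**Working it through.** The plan gives no sample size, expected rate or margin for this comparison, so there is no planned figure to reproduce. The check has two parts.

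**1. Reading the rule against the procedure.** The label is set by the main section or AUI device (SAP 4.3). A bifurcated implant adds two limbs, each component is introduced separately, the contralateral gate is cannulated, and the iliac criteria apply on both sides (SAP 3.1; Protocol B.2.1 and D.1). An AUI needs one side. The label is therefore complete for a single-access AUI subject and for a bifurcated subject with the same method on both sides. It is incomplete only for a bifurcated subject with two methods.

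**2. Illustrating the effect.** All inputs are assumptions: per-site risk *a* = 3% (percutaneous) and *b* = 8% (cut-down), two independent sites per bifurcated subject, and mixed shares *m*P and *m*C within the percutaneous and cut-down labels.

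Risk of at least one access-site complication per subject:

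- bilateral percutaneous: 1 − 0.97² = 5.91%
- mixed: 1 − 0.97 × 0.92 = 10.76%
- bilateral cut-down: 1 − 0.92² = 15.36%

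The unmixed difference is 15.36 − 5.91 = 9.45 points.

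Under the main-device label, the observed difference is

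9.45 − *m*C × (15.36 − 10.76) − *m*P × (10.76 − 5.91) = 9.45 − 4.60 *m*C − 4.85 *m*P.

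| Mixed share | Percutaneous label | Cut-down label | Difference (points) |
|---|---|---|---|
| none | 5.91% | 15.36% | 9.45 |
| 5% in both | 6.15% | 15.13% | 8.98 |
| 10% in both | 6.40% | 14.90% | 8.50 |
| 20% in both | 6.88% | 14.44% | 7.56 |
| 30% in both | 7.37% | 13.98% | 6.61 |
| 20% in cut-down only | 5.91% | 14.44% | 8.53 |
| 20% in percutaneous only | 6.88% | 15.36% | 8.48 |

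When the share *m* is the same in both labels, the formula reduces to 9.45 × (1 − *m*). When only one group is mixed, the loss is about half of that.

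Other assumed risks behave alike. With *a* = 5% and *b* = 10%, the difference falls from 9.25 to 7.40 points at 20% mixed in both groups. Swapping *a* and *b* reverses the sign and leaves the shrinkage unchanged.

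At 20% mixed in both groups, the fraction of site complications in the percutaneous column that arose at cut-down sites is *mb* / [(2 − *m*)*a* + *mb*] = 0.016 / (0.054 + 0.016) = 23%.

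For scale, assume 70 subjects per group. The 95% half-width around 5.91% versus 15.36% is 1.96 × √[(0.0591 × 0.9409 + 0.1536 × 0.8464)/70], about 10 points. The shift at 20% mixed in both groups is 9.45 − 7.56 = 1.89 points.

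**The case against.** The strongest reply is that misattribution is inferred rather than stated. SAP 4.3 does not say that contralateral events are counted, or whether counting is per subject or per site. The table shells are a separate attachment (SAP 12.2) and could contain a per-site rule. This stands as a limit: the visible text lacks the rule, and the shells could supply it.

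Several stronger readings are tempting and not supported:

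- A reader might take the unilateral/bilateral line in SAP 5 as proof that mixed access is expected. It is not, because unilateral percutaneous access can also describe an AUI subject.
- A reader might call the label a unit-of-analysis error. It is an openly stated subject-level definition, and it answers a fair question about subjects whose main device was delivered by a given method. The gap lies in using it to attribute events at another site.
- A reader might conclude that the attenuation equals the mixed share. That holds only if the share is the same under both labels.
- A reader might ask for a per-site model with clustered intervals. Protocol H.1 plans no inference for secondary or additional endpoints, and nothing visible shows that the side of each complication is collected.

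It is also fair to say that the comparison is descriptive, that access was not randomized (so patient selection affects the contrast whatever label is used), and that the illustrated shift is small against the sampling error. Protocol L.9 records that no PMA-related analysis is scheduled any longer. However, SAP 1 makes these analyses the basis of the Clinical Study Report, and the access-complication comparison is not itself tied to the PMA submission. These points set the severity. They do not remove the gap in the wording.

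**Conclusion.** The point holds as a gap in a descriptive analysis. Followed as written, SAP 4.3 puts contralateral events of mixed-access bifurcated subjects under the other method, which draws the two columns together whenever the per-site risks differ. Bifurcated subjects with one method on both sides and single-access AUI subjects are unaffected, and with no mixed subjects there is no distortion.

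The size is unknown because the documents do not give the mixed share. The 9.5-point difference falling to 7.6 points, or to about 8.5 points if only one group is mixed, rests on assumed risks of 3% and 8%, independent sites and a 20% share. The two primary endpoints, their significance level, the sample size and study success do not depend on it. Low severity; a cheap improvement.

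**What to change.** In SAP 4.3, tabulate access-site complications and access conversions descriptively for three groups of bifurcated subjects: bilateral percutaneous, mixed, and bilateral cut-down. Show single-access AUI subjects separately. Keep the main-device label as a secondary display.

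Where the side of a complication is recorded, add a table of events by the method used at their own site, with the number of sites as denominator. Add no inferential testing.

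The three-group table needs the access method on each side, which the unilateral/bilateral summary in SAP 5 already largely requires. The work is a change of SAP wording and modest programming. The downside is smaller groups. The per-site table depends on whether the side of each event was captured. Enrollment has ended, so it should be produced only where that information exists.
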